11. PROCEDURES INVOLVED*

Randomization. Two groups of two practices (4 practices in total) will be matched based on comparable size and percent of minority patients. Within each pair, practices will be randomly allocated to Asthma Link or the comparison condition, using a computerized function. This will result in two practices randomized to the Asthma Link condition and two practices randomized to the Enhanced Usual Care comparison condition.

Recruitment will be performed from each practice site until the target n=72 parent-child dyads (18 per site) are recruited. (see section 13 on “Sample size calculation”) Recruitment will begin during the 2021-2022 academic school year.

Procedure Steps:

1. Research coordinator (RC) identifies potentially eligible patients (children aged 6-17 years (enrolled in grade 1-12) years and prescribed a daily inhaled corticosteroid per medical record from most recent visit scheduled for a clinic visit) through the practice's office scheduling and medical record system (e.g., Epic). RC will also collect that patient's name, DOB, mailing and email addresses, phone number, insurance type (as a proxy for socioeconomic status), list of

INVESTIGATOR STUDY PLAN

medications, number of emergency room visits, number of hospital admissions and number of oral steroid courses for asthma relief.

2. RC creates a Lilac Form for any potentially eligible patients as described above. (Lilac form is an indicator to the medical provider seeing the patient that this patient is potentially eligible for study.)

3. Asthma Link condition: As part of clinical practice, medical provider will determine if patient is struggling with taking daily asthma medicine. If YES, then will introduce Asthma Link by saying “There is a clinical program that allows for your child to receive their daily asthma medicine at school supervised by the school nurse.” Child can be enrolled in Asthma Link per the usual clinical steps (see Asthma Link steps).

- After they are enrolled in Asthma Link, medical provider will give family one-page description of study (see Flyer) and state “Researchers at UMass are performing a study of children who are participating in Asthma Link, would you be interested in hearing more?”

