12. DATA AND SPECIMEN BANKING*

N/A

13. Data Analysis and Management*

Sample size calculation

In order to obtain a sample size of 72 parent-child dyads to complete the research, we will potentially enroll up to 100 parent-child dyads. Because pilot studies do not provide meaningful estimates of effect sizes for between-condition comparisons, due to the imprecision inherent in data from small samples^{19,20} we base our proposed sample size of 72 parent-child dyads (36 per condition, 18 per practice) on pragmatics of recruitment, retention and the necessities for examining feasibility, providing important information for design and recruitment for the future R01 study to test the impact of Asthma Link™ in a large cluster RCT. We will identify refinements required to implement the large cluster RCT by obtaining data about several process outcomes as well as feasibility of recruitment, retention, engagement, fidelity and assessment procedures of Asthma Link™.

Taking estimation of retention rate as an illustrative outcome, and applying an intra-class (pediatric practice) correlation of 0.01, similar to the value of 0.006 from [name] prior studies of school-based teen smoking, the resulting design effect= $1.19 = 1 + [1 + 0.01 \times 9]$ ²¹ yields an effective sample size of $20/1.09 \approx 18$ dyads/condition. For a conservatively low retention rate of 80%, lower than the 97% observed in [name] previous FITLINE study,¹⁸ we can estimate a 95% confidence interval for retention percent of (51.9%, 95.7%) for each practice separately or (68.9%, 88.5%) combining all 4 practices. A sample of 18 dyads per practice (36 per condition) yields 95% confidence intervals for practice ICC of (0.018, 0.094) for a conservatively large true ICC=0.05.²² Because estimates from pilot studies alone tend to be underpowered due to the variability in estimated standard errors,^{19,20} we will combine our results (including the ICC) with clinically meaningful effect and results of previous adequately powered interventions to calculate sample size requirements for our large cluster RCT. Data from the recruited pediatric practices show that 5-7 very poorly controlled asthmatics are seen per month.

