Statistical Analysis: To assess feasibility outcomes in Aim 1, we will estimate parameters relevant for planning a larger study, including standard deviations of outcomes and ICC. We will also conduct preliminary analyses of the impact of Asthma Link™ on asthma outcomes. We will compare participants in the two arms (Asthma Link™ and comparison group), using methods such as parametric or nonparametric t-test or Poisson regression, depending on the observed outcome distribution. Some outcomes may have a Poisson distribution, such as hospital admissions, while spirometry values may be continuous. Intent-to-treat and completer analyses will be performed. The data collected in this proposal will provide estimates of trial retention, ICC, standard deviation, and effect size. We will use these and data published in the literature to estimate sample size for a larger trial. The secondary outcomes analyses of asthma health outcomes will be exploratory by necessity given the pilot nature of this study.

INVESTIGATOR STUDY PLAN

Data will be collected at baseline (study entry), and at 3-, 6-, and 12-month follow-up in the privacy of the parent/child's home as the parent/child survey will be sent through email, in the pediatric practice staff's office or home (for pediatric provider and asthma champion surveys which will be sent through email), in the school nurse office or home (for school nurse surveys which will be sent through email). Assessments will be pre-tested to ensure the time burden does not exceed 30 minutes. The parent/student survey and assessment tools for this study will be adapted from [name] prior adolescent smoking cessation trials and our pre/post study^{14,18}. Data confidentiality will be emphasized on the surveys and verbally by Research Coordinator, and by the use of a unique study identification number.

Data Management: The surveys will be conducted either over the phone or by using the REDCap™ system, a nationally used secure, web-based database application (<http://project-redcap.org>) that provides: 1) an intuitive interface, 2) audit trails for tracking data manipulation and export, 3) procedures for importing data from external sources, 4) easy development of web survey tools and 5) automated export procedures to various statistical packages.

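### Practices are randomised in two matched pairs, but only child-level methods are named for comparing health outcomes, so standard errors and p-values will generally be too small

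*Combined protocol and SAP*

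**What the plan says.** Section 11 (Randomization) makes the practice the unit of allocation. Four practices form two pairs that "will be matched based on comparable size and percent of minority patients", and "Within each pair, practices will be randomly allocated to Asthma Link or the comparison condition". Each arm therefore holds two practices, with a target of 18 parent-child dyads in each.

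Section 13 (Statistical Analysis) works at a different level. It states "We will compare participants in the two arms", "using methods such as parametric or nonparametric t-test or Poisson regression, depending on the observed outcome distribution". It names no practice or pair term, mixed model, generalised estimating equation, cluster-robust standard error or practice-level summary.

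The plan does recognise practice-level correlation elsewhere. Section 13 (Sample size calculation) illustrates the precision of retention by "applying an intra-class (pediatric practice) correlation of 0.01", "similar to the value of 0.006" from earlier school-based smoking studies. It takes 0.05 as a deliberately large value when discussing how precisely the ICC can be estimated. The Statistical Analysis paragraph lists the ICC among the quantities to be estimated for the next trial: "The data collected in this proposal will provide estimates of trial retention, ICC, standard deviation, and effect size". It also limits the weight of the health comparisons: "The secondary outcomes analyses of asthma health outcomes will be exploratory by necessity given the pilot nature of this study".

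**The concern.** Children in the same practice share clinicians, habits of care and a catchment, so their outcomes may be correlated. When whole practices are allocated, that correlation adds to the variance of the difference between arms. A child-level t-test or plain Poisson regression leaves most of it out and so tends to report intervals that are too narrow and p-values that are too small.

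What is at stake is the stated uncertainty of the health-outcome comparisons, and of any effect size carried into planning the larger trial. Section 13 promises no intervals or significance claims for these outcomes, but the methods it names produce standard errors and p-values as a matter of course.

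**Working it through.** **The plan's own figures.** The plan prints no figure for the arm comparison. Its only numerical allowance for clustering is in the retention illustration, where a design effect printed as 1.19 is applied as 1.09. The applied value reproduces as 1 + 0.01 × 9 = 1.09, which corresponds to clusters of 10. At the planned 18 per practice it would be 1 + 0.01 × 17 = 1.17. That discrepancy is a separate matter and nothing below depends on it.

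**Inputs.** Two pairs, one practice per arm in each pair (section 11). Children per practice m = 18 (sections 11 and 13), with 13 (section 24) and 25 (section 25) as alternatives. ICC r = 0.006, 0.01 and 0.05 (section 13). Assumed: that these ICCs carry over to asthma outcomes, a two-sided 5% level, a normal outcome, and a share s of the between-practice variance that is common to a pair and so removed by matching. The documents do not give s.

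**Step 1: variance of the arm difference** (total variance 1).
- True: r(1 − s) + (1 − r)/m
- Expected from the pooled child-level t-test: (1 − r)/m + r/(2m − 1)

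With m = 18 and s = 0:
- r = 0.006: 0.0612 against 0.0554, so the standard error is too small by a factor of √1.105 = 1.05
- r = 0.01: 0.0650 against 0.0553, factor 1.08
- r = 0.05: 0.1028 against 0.0542, factor 1.38

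**Step 2: when the problem disappears.** The two variances are equal when 1 − s = 1/(2m − 1). At m = 18 this is 1/35, so s = 34/35, about 97%, whatever the ICC. Only above that share is the child-level standard error not too small.

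**Step 3: true error of the t-test.** Simulated null trials, 70 degrees of freedom, m = 18:

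| Variance removed by matching | ICC 0.006 | ICC 0.01 | ICC 0.05 |
|---|---|---|---|
| None | 6.2% | 7.0% | 15.2% |
| Half | 5.6% | 6.0% | 10.0% |
| All | 5.0% | 5.0% | 4.7% |

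With no benefit from matching, ICCs of 0.01 and 0.05 give about 6.4% and 12.3% at 13 per practice, and 7.8% and 18.9% at 25.

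**Step 4: counts.** Poisson regression was simulated with gamma practice effects, no child-level overdispersion, m = 18 and s = 0. At an assumed mean of 0.5 to 4 events per child, the error is about 6%, 7% and 15 to 16% at the three ICCs. At an assumed 0.1 events per child it is only about 1.5% (ICC 0.01) and 5% (ICC 0.05), because the Wald test is itself conservative with so few events.

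**Step 5: what a remedy can do.** Multiplying a continuous-outcome standard error by √(1 + (m − 1) × ICC) gives √1.17 = 1.08 and √1.85 = 1.36 at ICC 0.01 and 0.05. With s = 0 and the true ICC equal to the one used, coverage is 95.0% and 94.7%. The 0.01 version covers only 87.8% if the true ICC is 0.05. For counts the multiplier is not safe. With assumed child-level overdispersion (squared coefficient of variation 1), the widened Poisson interval covers about 90% at a mean of 0.5 and 73 to 74% at a mean of 2. A paired t-test on the two within-pair differences holds 5.0%, but with 1 degree of freedom its critical value is 12.71, against 1.99 for 70.

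**The case against.** The strongest reply is that little turns on this. The primary trial outcomes are recruitment, retention and fidelity. The health comparisons are labelled exploratory, with no alpha or power attached. Section 13 itself says that pilots do not give meaningful between-condition effect sizes, and it plans to combine the results with clinically meaningful effects and earlier adequately powered trials. At the planning ICC of 0.01 the error is 7.0% rather than 5%. All of this stands, and it limits the harm. It does not supply a method that fits the design.

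The list of methods is also open-ended. A reader might infer that the plan commits to unadjusted inference; the wording does not go that far. The gap is that no section tells the analyst to account for practice or pair.

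A reader might also infer that every standard error will be too small. That is too strong, as steps 2 and 4 show: near-complete removal of practice variance by matching, or very rare events, takes the inflation away. Hospital admissions, the plan's own example of a Poisson outcome, might be that rare. However, matching uses only practice size and percentage of minority patients, so near-complete removal should not be assumed.

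Finally, the ICCs are borrowed: 0.01 and 0.006 from a retention illustration, 0.05 from a discussion of ICC precision. None was estimated for asthma outcomes. That objection stands, and the error figures are a range under assumptions.

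**Conclusion.** The point holds in limited form. The methods named for the health outcomes do not match randomisation by practice within pairs. Unless matching removes about 97% or more of the between-practice variance, their standard errors and p-values will generally be too small, with very rare counts as an exception. With 18 per practice, a 5% level and no benefit from matching, the true error is about 6.2% to 7.0% at ICCs of 0.006 to 0.01, and 15.2% at 0.05. If matching removes half of the practice variance, it is 5.6% to 6.0%, and 10.0%.

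The documents do not support reading 15.2% as the trial's actual error rate, since it needs both the largest borrowed ICC and no gain from matching. Nor do they support a claim that the effect estimates are biased by this or that the feasibility conclusions are weakened. The wording should still be changed, because the analysis as written ignores the design and the change is cheap.

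**What to change.** In section 13 (Statistical Analysis), keep the choice of summary by outcome distribution (means or event rates) and replace the child-level comparison with:

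> Between-arm comparisons of asthma health outcomes are descriptive, with no claims of significance. Results will be shown for each of the four practices and as differences (or log rate ratios) within each matched pair. Any child-level interval will be labelled as not accounting for randomisation by practice or, for continuous outcomes, widened by the square root of 1 + (m − 1) × ICC, where m is the number analysed per practice, at assumed ICCs of 0.01 and 0.05. If any test is reported, it will be a paired t-test on the two within-pair differences in practice summaries (1 df).

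The multiplier should not be applied to plain Poisson standard errors, because it does not correct child-level overdispersion. With two practices per arm, a more elaborate cluster model would be no more reliable.

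The cost is slightly more analysis and no new data. Widened intervals grow by 8% (ICC 0.01) and 36% (ICC 0.05) at 18 per practice, and are conservative if matching works well. The paired test has almost no power.

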We anticipate that recruitment of n=72 dyads will take 18 months based on [name] FITLINE study ¹⁸. We do not anticipate issues with this recruitment based on prior recruitment of families for Asthma Link™ from the Worcester community in our pre/post study and based on prior recruitment from these same pediatric practices in the FITLINE study. (also see page 19 which describes estimated number of asthmatics in proposed Pediatric practices, demonstrating feasibility of recruitment). The Institutional Review Board will review all research procedures and protocols. All instruments will be submitted to the IRB for review and approval prior to use.

We will not enroll any participants in the study prior to receiving IRB approval.

SURVEY – PARENT AND CHILD – 20 MINUTES _See uploaded parent baseline, parent 3 month, parent 6 month, and parent 12 month surveys.

The 4 parent surveys will include the following constructs: Patient Health Outcome questions including the Asthma Control Test (ACT; measure of severity of asthma symptoms) and the Maximum Asthma Symptom Days (MSD), Emergency Department visits, hospital admissions, school absences, oral steroid usage and pharmacy refill data. The Baseline survey will include demographic questions that ask about the parent's age, sex, race/ethnicity, relation to the child participating in the study, education, marital status, tobacco usage, health insurance, contact information, family functioning, comorbidities, income, and average monthly as a proxy for socioeconomic status. The 3 month, 6 month, and 12 month follow up surveys for the Asthma Link™ condition will also include the following constructs: acceptability, cost, and sustainability. All surveys will be completed either on-line using RedCap (Please see data management) or over the phone with the Research Coordinator. We are using emails and/or phone calls to deliver/collect these surveys. As soon as the baseline survey has been completed, those completing the survey via email will be automatically sent out future surveys.

SURVEY – SCHOOL NURSE – 10 MINUTES _See uploaded school nurse baseline and end-of-intervention surveys.

The school nurse survey will include the following constructs: acceptability, cost, and sustainability. All surveys will be completed either on-line using RedCap (Please see data management section) or over the phone with the research coordinator. We are using emails and/or phone calls to deliver and collect these surveys.

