SURVEY – MEDICAL PROVIDER – 5 MINUTES _See uploaded medical provider baseline and end-of-intervention surveys. The medical provider survey will include the following constructs: acceptability, cost, and sustainability. All surveys will be completed either on-line using RedCap (please see data management section) or over the phone with the research coordinator. We are using emails and/or phone calls to deliver and collect these surveys.

SURVEY- ASTHMA CHAMPION- 5 MINUTES _See uploaded asthma champion baseline and end-of-intervention surveys. This will include the same constructs of acceptability, cost and sustainability. Surveys will be completed either on-line using RedCap (please see data management section) or over the phone with the research coordinator. We are using emails and/or phone calls to deliver and collect these surveys.

INVESTIGATOR STUDY PLAN

We will be accessing the practice's medical record system (same system as above, e.g., Epic) to obtain documentation of the child's emergency room visits, hospital admissions, and oral steroid courses at the baseline time point (recording the number of events for the 6 months prior), 3 month, 6 month, and 12 month time points (recording the number of each of these events for the 3 or 6 months prior.). This data will also be collected 12 months following the completion of the 12 month survey in order to observe for sustained impact on health outcomes and to see if engagement in Asthma Link continues beyond one year. This data will be directly put into the RedCap database without any downloading of information. (please see data management section)

We will be contacting the child's pharmacy to obtain refill history of their daily ICS medication at baseline (obtaining the number of refills for the prior 6 months), 3, 6, and 12 months, and 12 months following the completion of the 12 month survey to assess for medication adherence. This data will be entered directly into the REDCap database.

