Portable Spirometry: At baseline, 3, 6, and 12 months the child will perform spirometry in the school nurse's office. The Research Coordinator will perform portable spirometry in the school at the time that the student normally reports to the nurse for their daily asthma medication so as not to disrupt the child's school activities. Given that the spirometry test takes less than 3 minutes to complete for each child, we are confident that it will not pose a disruption to the child's school activities. The Research Coordinator will enter the spirometry data into RedCap for each participant without downloading any data.

School absence data will be collected through school nurse report and will be recorded from the school nurse on the School Nurse checklist and faxed to the Research Coordinator.

Asthma Link Condition: Those practices that are randomized to the Asthma Link group will receive pediatric pulmonologist delivered trainings for pediatric practices on behavioral strategies to help promote asthma medication adherence and a 1 hour training on the Asthma Link clinical program and how to enroll children in Asthma Link (reviewing the steps of this clinical program- see "Asthma Link Clinical Program Steps") and carry out this evidenced-based program in the context of their clinical practice (reviewing the steps to Asthma Link and answering any questions they may have).

Comparison Condition: Those practices that are randomized to the Enhanced Usual Care Comparison Group will receive pediatric pulmonologist delivered trainings for pediatric practices on behavioral strategies to help promote asthma medication adherence. These include training to counsel patients on the strategies such as the placement of cell phone alarms to remember to take their daily medicine and placement of an elastic band around the inhaler and the toothbrush so that a child always remembers to take their daily inhaler before brushing their teeth. We thought it ethically important to provide more than just usual care to the 2 pediatric practices assigned to the comparison condition.

Families who agree to participate in the study from either the Asthma Link or Enhanced Usual Care practices will receive a mailed "Asthma Workbook" to aid in their understanding of asthma, support their asthma care and help with daily medicine adherence (See Asthma Workbook)

INVESTIGATOR STUDY PLAN

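### The exploratory comparison of health outcomes gives no role to the baseline values the trial collects, although a baseline-adjusted regression would generally be more precise at almost no cost

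*Combined protocol and SAP*

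**What the plan says.** The Statistical Analysis paragraph of section 13 says the two arms will be compared "using methods such as parametric or nonparametric t-test or Poisson regression, depending on the observed outcome distribution". It names no covariate, no practice or pair term, no repeated-measures model and no time point. It does not say whether the response is the follow-up value or the change from baseline.

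The same section sets the schedule: "Data will be collected at baseline (study entry), and at 3-, 6-, and 12-month follow-up". Section 11 shows that baseline values of the health outcomes are part of it:

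- **Parent surveys, including baseline:** "The 4 parent surveys will include the following constructs: Patient Health Outcome questions including the Asthma Control Test". Symptom days and school absences are on the same surveys.
- **Medical record counts** of emergency visits, admissions and oral steroid courses: "at the baseline time point (recording the number of events for the 6 months prior". Refills are also obtained for the 6 months before baseline.
- **Spirometry:** "At baseline, 3, 6, and 12 months the child will perform spirometry in the school nurse's office".

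The planned size is "72 parent-child dyads (36 per condition, 18 per practice". Section 11 (Randomization) forms two pairs of practices, matched on size and percent minority, and randomizes within each pair. Section 13 calls the health-outcome analyses exploratory. It also says that the SD and effect size from this study will help to size a larger trial.

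**The concern.** A two-sample t-test or rank test by arm cannot take a baseline covariate. Used on follow-up values, it leaves in the error term all the between-child variation that the baseline value could explain. Used on change scores, it generally over-corrects. In both cases part of any baseline difference between the arms enters the estimate.

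Such differences are likely here. There are only two practices per arm, and the matching does not cover any asthma measure. What is at stake is the precision of the exploratory effect estimates and the usefulness of the variance figures passed to the larger trial.

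**Working it through.** **The plan's own figure.** The documents give no power, SD or effect size for any health outcome. The nearest precision figure is the section 13 interval for 80% retention over all four practices, (68.9%, 88.5%). An exact binomial interval with n = 72 and x = 0.8 × 72 = 57.6 reproduces it, without a design effect. This confirms that 72 is the number to work with.

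**Inputs from the documents.** 36 per arm, 18 per practice, two practices per arm; ICC 0.01 (planning value) and 0.05 (large value), both from section 13.

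**Assumed inputs.** The baseline-to-follow-up correlation r is not in the documents; 0.3, 0.5 and 0.7 are used. Event rates and dispersion are assumed below. Outcomes are in SD units.

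**Step 1: chance difference at baseline.** Design effect = 1 + (18 − 1) × ICC, which is 1.17 or 1.85. The SD of the arm difference in baseline means is √(2/36 × design effect):

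- ICC 0.01: √(0.0556 × 1.17) = 0.255
- ICC 0.05: √(0.0556 × 1.85) = 0.321

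The chance of a difference above 0.25 SD in either direction is then about 33% or 44%. Any gain from matching is ignored.

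**Step 2: precision of the three analyses.** Clustering is ignored, as the named t-test ignores it. The standard errors (SE) are √(2/36) = 0.236 for follow-up values, 0.236 × √(2(1 − r)) for change scores and 0.236 × √(1 − r²) for baseline adjustment.

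| r (assumed) | Follow-up SE | Change SE | Adjusted SE | Variance cut v follow-up (r²) | Variance cut v change ((1 − r)/2) | Equivalent n per arm (36/(1 − r²)) |
|---|---|---|---|---|---|---|
| 0.3 | 0.236 | 0.279 | 0.225 | 9% | 35% | 39.6 |
| 0.5 | 0.236 | 0.236 | 0.204 | 25% | 25% | 48.0 |
| 0.7 | 0.236 | 0.183 | 0.168 | 49% | 15% | 70.6 |

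If the same correlation holds between practices as within them, the clustered SE falls by the same factor. At r = 0.5 it goes from 0.255 to 0.221 (ICC 0.01) or from 0.321 to 0.278 (ICC 0.05).

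**Step 3: counts.** Take a gamma-Poisson model with yearly mean m, dispersion k = 1, a baseline of T years and a follow-up of one year. The share of follow-up variance explained by the baseline count is (m²T)² / [(mT + m²T²)(m + m²)].

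- m = 1: T = 0.5 gives 0.25/(0.75 × 2) = 17%; T = 1 gives 1/(2 × 2) = 25%.
- m = 0.2: T = 0.5 gives 0.0004/(0.11 × 0.24) = 1.5%; T = 1 gives 0.0016/(0.24 × 0.24) = 2.8%.

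For rare events the baseline count helps little, and a longer look-back adds little.

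**Step 4: is the baseline taken before exposure?** In section 11 (step 3), children at Asthma Link practices join the clinical program before they hear of the study; section 14 (DSMB paragraph) says the same. Section 11 then times spirometry for when the child usually comes to the nurse for the daily medicine. Survey and FEV1 baselines in that arm may therefore follow the start of supervised dosing, and adjusting for such a value could remove part of the effect. Record and refill data can be dated back to avoid this.

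**The case against.** **The text does not state an unadjusted analysis.** The list of methods is open-ended, and Poisson regression can carry a baseline covariate. A reader might infer that follow-up values will be compared without adjustment. The documents do not say so, and this objection stands. What remains is that no section gives the baseline values a role and that two of the three named methods cannot use them.

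**Imbalance is not a second harm.** A reader might count the chance shift from unequal practices on top of the lost precision. At r = 0.5 and ICC 0.01 the shift has SD 0.5 × 0.255 = 0.127, and (0.127/0.255)² = 0.25 = r². It is the same loss and is already within the unadjusted SE.

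**The larger trial need not be oversized.** A reader might infer that an unadjusted SD inflates its size by 1/(1 − r²), that is by 10%, 33% or 96%. That requires the larger trial to adjust for baseline and to take its SD from this pilot alone. No section says it will adjust, and section 13 says pilot results will be combined with a clinically meaningful effect and outside data.

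**Adjustment does not solve clustering.** This also stands. A test that ignores practice turns a nominal 5% into about 7% (ICC 0.01) or 15% (ICC 0.05), and adjusting for baseline does not by itself repair that. It removes only practice differences tied to the measured baseline.

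**The stakes are limited.** The primary outcomes in section 4 are recruitment, retention and fidelity, and section 13 itself disclaims meaningful effect sizes from pilots. That limits the weight of the point, but the remedy is mainly wording.

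**Conclusion.** The concern holds as an omission with a better and nearly free alternative. Baseline values are collected, the between-arm comparison does not use them, and either form of response left open by section 13 is generally less precise than baseline adjustment.

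Against follow-up values alone, the loss runs from small to substantial depending on r, which is assumed throughout. It is negligible for rare events. The imbalance range rests on the plan's own ICCs and on 18 children per practice. The effect falls on the exploratory estimates and the variance figures carried forward, not on feasibility conclusions. The change is recommended rather than essential.

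**What to change.** In the Statistical Analysis paragraph of section 13:

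1. State that each health outcome with a baseline value is compared by regression on arm and the child's own baseline value: linear for ACT, symptom days and FEV1; a count model with the baseline count for events and refills. Account for the matched pair and practice.
2. Date record and refill baselines to before the first supervised dose. For ACT, symptom days and FEV1, record whether the baseline came before supervised dosing. Where it may not have, present the adjusted result beside the unadjusted one.
3. Report the unadjusted SD, the adjusted SD and the baseline-to-follow-up correlation, so that the larger trial can be planned either way.
4. State a rule for children with no baseline value.

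The cost is SAP wording, one extra item on baseline timing, one or two degrees of freedom for the baseline term, and the missing-baseline rule. That rule needs some care, because usable pre-dose survey and spirometry values may be lacking mainly in the Asthma Link arm. Adding age as a covariate and extending the record look-back from 6 to 12 months are optional.
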